In preliminary work, we have shown that we can quantitatively measure myocardial blood flow reserve, oxidative metabolism and myocardial fibrosis through non-invasive cardiac imaging. Myocardial blood flow reserve can be quantitatively measured with cardiac magnetic resonance imaging (cMRI) and positron emission tomography (PET). The mono-exponential

decay rate (K_{mono}) of ^{11}C -Acetate determined with PET is a validated measure of myocardial oxidative metabolism. Fibrotic myocardium can be quantified using cMRI T1 mapping.

We postulate that reduced myocardial blood flow reserve contributes to impaired oxidative metabolism and increased myocardial fibrosis in HFpEF. We propose to test the following primary hypotheses: 1) Compared to healthy and hypertensive individuals, subjects with HFpEF have reduced myocardial blood flow reserve, 2) Compared to healthy and hypertensive individuals, subjects with HFpEF have reduced oxidative metabolism; 3) Compared to healthy and hypertensive individuals, subjects with HFpEF have increased myocardial fibrosis, and 4) Myocardial blood flow reserve is positively correlated with oxidative metabolism and inversely correlated with myocardial fibrosis.

Aim 1. To compare myocardial blood flow reserve in individuals with HFpEF versus those with hypertension and healthy individuals. We will enroll 60 subjects (20 HFpEF, 20 hypertensive, and 20 healthy) who will undergo cMRI and ^{13}N -Ammonia PET to quantify myocardial blood flow at rest and during pharmacologic stress with regadenoson.

Aim 2. To compare myocardial oxidative metabolism in individuals with HFpEF versus those with hypertension and healthy individuals. Subjects enrolled in aim 1 will also undergo ^{11}C -Acetate PET imaging to quantify oxidative metabolism via the mono-exponential decay rate of ^{11}C -Acetate.

Aim 3. To compare myocardial fibrosis in individuals with HFpEF versus those with hypertension and healthy individuals. Subjects enrolled in aim 1 will also undergo cMRI with T1 mapping to quantify myocardial fibrosis.

Aim 4. To assess the relation between myocardial blood flow reserve, oxidative metabolism and fibrosis. The correlations between myocardial blood flow reserve, oxidative metabolism and fibrosis will be evaluated.

2. Study Design

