13N-Ammonia Positron Emission Tomography for the assessment of myocardial blood flow. 13N-Ammonia studies will be performed at rest and stress on a whole body PET/CT scanner as previously described.³⁸ An initial transmission scan will be obtained for the purpose of attenuation correction. Next, rest imaging will be initiated in list mode upon injection of 25mCi of intravenous 13N-Ammonia with serial images acquired over approximately 15-20 minutes. Approximately 50 minutes after the initial 13N-Ammonia injection (5 half-lives), imaging will be repeated following pharmacologic vasodilation with regadenoson (Astellas Pharma, Northbrook, IL). As with the cMRI protocol, 400 µg of regadenoson will be injected intravenously over 5-10 seconds, followed by a 5-10 ml saline flush. Approximately 60 seconds after the regadenoson injection, 25mCi of 13N-Ammonia will be injected with PET imaging in list mode. Heart rate, rhythm, and blood pressure will be monitored throughout the imaging protocol. Myocardial blood flow and coronary flow reserve will be quantified off-line using FlowQuant software (Ottawa Heart Institute, Ottawa, Canada).

Procedure/Activity	Frequency
Informed Consent	Once (at time of screening in clinic)
Blood draw	Once (at beginning of study visit – day 1)
Peripheral IV placement	Twice (at study visit on days 1 & 2)
Transthoracic Echocardiogram with contrast	Once (at study visit – day 1)
¹¹C-Acetate PET	Once (at study visit – day 1)
Cardiac MRI (rest, stress)	Once (at study visit – day 1)
Cardiac MRI (fibrosis imaging)	Once (at study visit – day 2)
¹³N-Ammonia PET (rest, stress)	Once (at study visit – day 2)

Reporting of clinical findings. As the imaging studies are being performed for research purposes, clinical reports will not be generated. However, if unexpected or previously unknown abnormalities of clinical importance are identified or urgent/emergent conditions are found, these will be clinically reported to both the patient and the patient’s physicians.

3. Statistical Methods

Aim 1. To compare myocardial blood flow reserve in individuals with HFpEF versus those with hypertension and healthy individuals.

Primary Hypothesis: Compared to healthy and hypertensive individuals, subjects with HFpEF have reduced myocardial blood flow reserve.

Secondary Hypotheses:

- A) Myocardial blood flow is progressively impaired from healthy, to hypertensive, to HFpEF.

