- B) Myocardial blood flow reserve by Gd enhanced cMRI (MPRI) is correlated with CFR by ¹³N-Ammonia PET.
- C) Subendocardial MPRI is lower than subepicardial MPRI in HFpEF.
- D) Subendocardial MPRI is progressively impaired from healthy to hypertensive to HFpEF.
- E) Myocardial blood flow reserve is positively correlated with LV diastolic function.
- F) Myocardial blood flow reserve is positively correlated with LV systolic function.

Analysis for aim 1. Primary outcome: Myocardial blood flow reserve, as measured by MPRI from contrast enhanced cMRI first pass perfusion imaging and CFR from ¹³N-Ammonia PET perfusion imaging will be compared between the three study groups: healthy, hypertensives, and HFpEF. The distributions of each within each study group will be assessed using histograms, Q norm plots, and the Shapiro Wilk test. If normally distributed then analysis of variance will be used to test for differences in myocardial blood flow reserve between groups. If the p-value from the ANOVA is < 0.05, then pairwise comparisons using unpaired t-tests with unequal variances will be made between groups using a Bonferroni correction. If MPRI or CFR is not normally distributed, then a Kruskal-Wallis test and Wilcoxon rank sum tests will be used in place of ANOVA and t-tests. The null hypothesis is that myocardial blood flow reserve does not differ among HFpEF patients, healthy individuals, and hypertensive individuals. We will also assess correlations (Spearman) between myocardial blood flow reserve, age, gender, blood pressure, heart rate, and body mass index. To account for potential confounders, multivariable linear regression models will be constructed with myocardial blood flow reserve as the dependent variable, study group as the primary independent variable, with adjustments for age, gender, race/ethnicity, anti-hypertensive medications, systolic blood pressure, heart rate, body mass index, LVEF, LV end diastolic volume, and LV mass. Prior to entry into models, variables will be log transformed, as appropriate. We will check model fit by residual plots. Missing data will not be imputed as we will attempt to replace subjects with significant amounts of missing data due to uninterpretable images, as detailed above.

Statistical power for Aim 1: Using a one-way ANOVA at $p = 0.05$, we present between group differences in myocardial blood flow reserve as assessed by CFR under different sample size and power scenarios in **Table 4**. We anticipate

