Aim 3. To compare myocardial fibrosis in individuals with HFpEF versus healthy individuals and those with hypertension.

Primary Hypothesis: Compared with healthy and hypertensive individuals, subjects with HFpEF have increased myocardial fibrosis.

Secondary Hypotheses:

- A) Myocardial fibrosis progressively increases from healthy, to hypertensive, to HFpEF.
- B) Myocardial fibrosis is inversely correlated with LV diastolic function.
- C) Myocardial fibrosis is inversely correlated with LV systolic function.

Analysis for aim 3. Primary outcome: myocardial fibrosis assessed by T1 relaxation times by cMRI will be compared between the three study groups. The analyses for aim 3 will be the same as for aim 2, except that myocardial fibrosis, instead of oxidative metabolism, will be

compared. The distribution of T1 relaxation times, as a measure of myocardial fibrosis, within each study group will be assessed. Based upon distributions, ANOVA or Kruskal-Wallis tests will be used to identify differences between study groups and if significant $p < 0.05$, then pairwise comparisons with T-tests or Wilcoxon rank sum tests will be performed with Bonferroni correction. The null hypothesis is that T1 relaxation times do not differ among HFpEF, healthy, and hypertensive individuals. We will also check for correlations (Spearman) between myocardial fibrosis, age, gender, blood pressure, heart rate, body mass index, and resting myocardial blood flow. To account for potential confounders, multivariable linear regression models will be constructed with myocardial fibrosis as the dependent variable, with adjustments for the same covariates described for oxidative metabolism above.

Statistical power for Aim 3: Using an ANOVA at $p = 0.05$, we present between group differences in T1 relaxation times (msec) under different sample size and power scenarios in **Table 6**. We anticipate having 80% power to detect a between

Healthy	Sample size			Power			SD
	HTN	HFpEF	0.90	0.80	0.70		
20	20	20	70	60	54	60	
15	15	15	80	70	64	60	
25	25	25	60	54	48	60	

ANOVA calculations based upon mean estimated T1 relaxation time in HFpEF of 381 ± 51 msec.⁴¹

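### In Aims 1–3 the pairwise tests are Bonferroni-corrected after a three-group omnibus gate; with a Welch ANOVA gate the correction could be dropped, regaining power for the HFpEF contrasts at a familywise error of about 5% per outcome

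*Combined protocol and SAP*

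**What the plan says.** The study has three groups of 20: "We will enroll 60 subjects (20 HFpEF, 20 hypertensive, and 20 healthy". Under Analysis for aim 1, blood flow reserve "will be compared between the three study groups: healthy, hypertensives, and HFpEF".

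The testing rule has two steps. First comes the gate: "If the p-value from the ANOVA is < 0.05, then pairwise comparisons using unpaired t-tests with unequal variances will be made". Then the same sentence adds the correction: "pairwise comparisons using unpaired t-tests with unequal variances will be made between groups using a Bonferroni correction". Analysis for aim 2 repeats the rule for Kmono. Analysis for aim 3 does the same for T1 times: if the omnibus test is significant, "then pairwise comparisons with T-tests or Wilcoxon rank sum tests will be performed with Bonferroni correction". For non-normal data, "then a Kruskal-Wallis test and Wilcoxon rank sum tests will be used in place of ANOVA and t-tests".

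The number of comparisons used in the Bonferroni correction is not given. The Aim 1 primary hypothesis names both control groups: "Compared to healthy and hypertensive individuals, subjects with HFpEF have reduced myocardial blood flow reserve". Aims 2 and 3 are framed the same way. The power sections (Tables 4–6) cover only the omnibus ANOVA. No power is given for an HFpEF contrast at the corrected level.

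**The concern.** Two layers of multiplicity control are stacked on three comparisons. With three groups, if any two pairwise null hypotheses are true, all three means are equal, and that is exactly the hypothesis the gate tests. A gate that truly has level 0.05 therefore already limits the familywise error, and the pairwise tests that follow can each use 0.05.

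The contrasts that carry the extra penalty are HFpEF versus healthy and HFpEF versus hypertensive, which are the primary questions of Aims 1–3. With 20 per group there is little power to spare, and the stated 80% does not include the penalty. A real HFpEF difference could pass the gate and then fail at the corrected threshold.

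**Working it through.** **Inputs.** Three groups of 20; gate at 0.05; Aim 1 largest-to-smallest CFR difference 0.87 and SD 0.90; Aim 2 difference 0.010 and SD 0.010; Aim 3 difference 60 msec and SD 60 (all Section 3). Assumed: two-sided tests, normal data, divisor 3 (0.05/3 = 0.0167) with divisor 2 (0.025) as the range, and the position of the hypertensive mean, which the power sections leave open.

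**The plan's own figure.** For a one-way ANOVA with the middle group at the midpoint, λ = n·d²/(2·SD²) = 20 × 0.87²/(2 × 0.90²) = 15.138/1.62 = 9.34. The noncentral F on (2, 57) degrees of freedom gives 76.4% power against the stated 80%. With SD 0.88 (the table footnote) it is 78.4%, and by a large-sample chi-square 78.7%. With the middle group at an extreme it is 87.8%. For Aims 2 and 3, λ = 20 × 1²/2 = 10 and power is 79.3%, which agrees with 80%. The small Aim 1 gap is a separate matter and nothing below depends on it.

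**Power for the contrasts.** Simulation at the Aim 1 inputs with the plan's ANOVA gate kept, followed by Welch t-tests (300,000 trials or, in some cells, 200,000):

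| Hypertensive mean | Claim | Divisor 3 | Divisor 2 | No Bonferroni |
|---|---|---|---|---|
| Equal to healthy | each HFpEF contrast | 70.3% | 75.2% | 81.2% |
| Equal to healthy | both HFpEF contrasts | 56.4% | 63.5% | 74.6% |
| Midway | healthy vs HFpEF | 69.7% | 73.2% | 75.5% |
| Midway | hypertensive vs HFpEF | 17.5% | 21.8% | 30.7% |
| Midway | both HFpEF contrasts | 16.2% | 20.7% | 30.2% |
| Equal to HFpEF | healthy vs HFpEF | 70.4% | 75.2% | 81.2% |

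The loss for both contrasts with divisor 3 is 74.6 − 56.4 = 18.2 points if only HFpEF is low, and 30.2 − 16.2 = 14.0 points in the midway case. At the Aim 2 and Aim 3 inputs, hypertensive versus HFpEF (midway) is 19% as planned and 33% without Bonferroni. At 15 per group and a CFR difference of 1.05 it is 18.7% and 32.7%.

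**Familywise error for one outcome.** All three means are equal unless stated; n = 20 each unless stated.

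| SDs (healthy/hypertensive/HFpEF) | ANOVA gate, divisor 3 | ANOVA gate, no Bonferroni |
|---|---|---|
| Equal | 3.8% | 5.0% |
| Equal, one group far apart | 1.6% | 4.9–5.0% |
| CFR 0.68/0.88/0.90 (last assumed) | 3.6% | 5.1% |
| T1 38/38/51 (middle assumed) | at most 3.7% | 5.15% |
| T1 38/38/51, HFpEF n = 15 | 3.6% | 5.9–6.0% |
| Kmono 0.006/0.006/0.001 (middle assumed) | 3.2% | 6.0–6.1% |
| Ratio 1:1:2 (assumed), HFpEF n = 15 | 3.1% | 7.2–7.3% |

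Dropping both the gate and the correction would give 12.2%, so the gate is doing real work. With a **Welch ANOVA gate** and unadjusted Welch t-tests, the error is 4.9–5.1% in every case checked. Power for both contrasts is then 74% (only HFpEF low) and 30% (midway), so almost all of the gain is kept.

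**Rank branch.** A Kruskal-Wallis gate with unadjusted Wilcoxon tests gives 4.8% when all groups are equal and 4.6–5.3% when one differs (20,000 trials, Monte Carlo standard error about 0.15 points).

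**The case against.** The strongest reply is that the planned rule inflates no error, contradicts nothing in the documents, and is a defensible cautious choice for a small mechanistic study with several outcomes. All of that stands: this is a question of efficiency, and a sponsor who prefers the stricter rule may keep it.

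A reader might go further and infer that the Bonferroni step protects against nothing and can simply be struck out. The documents do not support that. The pairwise t-tests allow unequal variances while the gate pools them, so the gate is not assured to have level 0.05. In the unequal-SD cases above the correction is what keeps the error below 5%. Unequal group sizes are also plausible: lost subjects are replaced only where possible (Section 2.3), and the power sections consider a 25% reduction. The Kmono case is a weak input, since the SD of 0.001 is attributed to HFpEF before Table 5 and to HFrEF after it.

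A reader might also infer that the change rescues HFpEF versus hypertensive. It does not. If hypertensives lie midway, that contrast still has only about 31% power; sample size is the main limit. The larger gain assumes hypertensives resemble healthy subjects, whereas the plan hypothesises a gradient and cites CFR of 2.18 in hypertension against 3.17 in normals. At the larger T1 difference the plan cites (459 versus 381 msec, SD 60, midway), healthy versus HFpEF has 94% power as planned and 96% without Bonferroni, so little is lost there.

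**Conclusion.** The point holds as a low-cost improvement, not as an error in the plan. With a valid three-group gate the Bonferroni step is not needed for 5% familywise control within an outcome. At the Aim 1 design point it costs about 18 points of power for showing both HFpEF contrasts if only HFpEF is low (about 11 with divisor 2: 74.6 − 63.5), and about 14 points in the midway case (about 9–10 with divisor 2: 30.2 − 20.7).

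This rests on normal data with equal SD 0.90 for the power figures, two-sided tests, the assumed divisor, and the assumed hypertensive mean. It also requires a gate that respects unequal variances. With the ordinary ANOVA as gate, unadjusted tests can reach about 6–7%.

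**What to change.** In the analysis text of Aims 1, 2 and 3, replace the ordinary ANOVA gate with Welch's ANOVA and the Bonferroni clause with: *If the three-group Welch ANOVA (or Kruskal-Wallis test) is significant at 0.05, each pairwise comparison is tested at two-sided 0.05 (closed testing, three groups only); otherwise no pairwise claim is made.* Make the change before outcome data are seen by group.

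The cost is wording only, with no added subjects or procedures. Familywise error per outcome rises from about 2–4% to the nominal 5%. Control remains per outcome under either rule. For the two Aim 1 measures together (MPRI and CFR), the chance of any false pairwise claim when all groups are equal is about 8.8–10.0% with unadjusted pairwise tests, against 6.7–7.6% as planned (correlation 0.7 to 0, assumed). Across three independent tests at 0.05 it is 1 − 0.95³ = 14.3%. The plan should state that this multiplicity is left uncontrolled or handle it separately. The rule must not be carried over to analyses with more than three groups. If the sponsor keeps Bonferroni instead, the divisor should be stated and power given for the HFpEF contrasts at the corrected level.

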2.2 Recruitment of Study Sample

2.2.1 Cohorts Defined

Heart Failure Preserved Ejection Fraction (n=20). HFpEF patients will be aged 50 years or older, have a physician confirmed diagnosis of HF, be symptomatic (New York Heart Association class II or III), with a LVEF $\geq 50\%$ within the prior 6 months, and no prior history of LVEF $< 50\%$. HFpEF subjects will have evidence of elevated LV filling pressures by ≥ 1 of the following within the last 6 months: invasive cardiac catheterization LV end diastolic pressure or pulmonary capillary wedge pressure > 12 mmHg, plasma B-type natriuretic peptide > 100 pg/ml, or echocardiographic $E/e' > 15$. HFpEF patients with known coronary artery disease (CAD) or angina) will be excluded to reduce potential confounding. Patients with significant valvular (\geq moderate stenosis or regurgitation), pericardial, or congenital heart disease, or symptoms due predominantly to right heart failure and pulmonary arterial hypertension will also be excluded, as will those with an estimated glomerular filtration rate (eGFR) < 45 ml/min/1.73m². HFpEF patients in acute decompensated heart failure requiring intravenous diuretics, hospitalization, or use of intravenous vasoactive medications will be eligible for screening, but must be compensated at the time of the protocol visit. HFpEF patients will be recruited through the Vanderbilt Heart and Vascular Institute HFpEF program.

Healthy (n=20): We will enroll volunteers matched on gender to the HFpEF group. Healthy subjects will be free of known cardiovascular disease (HF or cardiomyopathy, CAD, valvular heart disease, pericardial disease, arrhythmias, stroke, peripheral arterial disease), cardiovascular risk factors (hypertension, DM, tobacco use, dyslipidemia, family history of cardiovascular disease, CKD, autoimmune disorder), or use of medications for cardiovascular disease or its risk factors. In addition, healthy individuals must have normal cardiac structure and function, to be confirmed by conventional transthoracic echocardiography at the time of the screening visit. We will use the "Research Studies" email sent to accounts at Vanderbilt University Medical Center and the Research Study Volunteer Program, a registry that enables identification of healthy volunteers.

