2.3 Study Procedures

Screening Visit: At the screening visit, which will take place at the Clinical Research Center, a medical history and physical examination will be administered with eligibility for the protocol determined (**Table 2**). A venous blood draw will be performed for measurement of the complete blood count and creatinine to assess inclusion and exclusion criteria. For healthy and hypertensive subjects, an echocardiogram will be performed at the screening visit to assess inclusion and exclusion related to cardiac structure and function, if an echocardiogram within the previous 6 months is not available. If the subject fulfills the inclusion criteria without exclusions to participation, a protocol visit will be scheduled through the Clinical Research Center (CRC).

Protocol Visit: There will be one protocol visit during which the subject will undergo testing as outlined in **Table 3**. After arrival at the CRC, the subject will undergo a history and physical examination. If any intervening medical events between the screening and protocol visits occurred that would exclude the subject from participation, then the subject will be withdrawn from the study. A venous blood draw will be performed for measurement of complete blood count, basic chemistry panel, B-type natriuretic peptide, and collection of plasma and serum for storage at -80°C for future assays of circulating biomarkers. If the subject is anemic (hemoglobin <10g/dL), or has an eGFR < 45ml/min/1.73m² according to the Modified Diet and Renal Disease equation then the subject will be withdrawn from the study. Women of child bearing potential will also undergo a serum pregnancy test. If the serum pregnancy test is positive, the subject will be withdrawn from the study. Eligible subjects will then undergo cardiac imaging as described below. For all imaging procedures, data will be deidentified with the exception of a randomly generated subject number, such that imaging data cannot be linked directly to subject data, particularly categorization as healthy, hypertensive, or HFpEF. This will ensure that the analyzing investigator will be blinded to study group.

Table 3. Protocol Visit	
Day 1	Day 2

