11C-Acetate Positron Emission Tomography for the assessment of oxidative metabolism. We will follow an established protocol for 11C-Acetate PET imaging previously used within our lab.⁶ An intravenous line will be placed in an upper extremity by trained personnel. The subject will then lie supine on the PET/CT scanner and heart rate and blood pressure will be recorded at baseline and every 5 minutes. A limited transmission CT scan of the chest will be performed for

attenuation correction. ^{11}C -Acetate (0.286 mCi/Kg) will then be injected intravenously and PET imaging will begin. ECG gated images will be acquired in list mode for 30 minutes and reformatted into images of 12 frames of 10 seconds each, 8 frames of 30 seconds, 4 frames of 60 seconds, 2 frames of 300 seconds, and 1 frame of 600 seconds. The ^{11}C -Acetate images will be processed following CT attenuation correction. If the images are uninterpretable due to factors such as patient motion, attenuation artifacts, and/or inability to accurately gate images with ECG, then the subject will be withdrawn from the study with attempts to replace the subject to maintain sample size. Regions of interest over the LV blood pool and LV myocardium from the last image of the study will be applied to all preceding frames. Counts in the regions of interest will be determined and expressed as counts/pixel. The blood pool and LV myocardium activities will be plotted against time. The mono-exponential clearance rate, defined as K_{mono} , will be determined by least-squares fitting of the linear portion of the time-activity curve. K_{mono} has previously been demonstrated to correlate with myocardial oxygen consumption.¹⁹⁻²¹ As the rate of cardiac metabolism may be influenced by cardiac demand, LV efficiency will be calculated as the work-metabolic index (WMI) using the equation $\text{WMI} = (\text{LVSVI} \times \text{SBP} \times \text{HR}) / K_{\text{mono}}$, where LVSVI is the LV stroke volume index (stroke volume/body surface area), SBP is systolic blood pressure, and HR is heart rate.²² In addition, oxidative metabolism may be influenced by blood supply, and therefore we will also assess myocardial blood flow through cMRI and PET as described below.

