Analysis for Aim 4: For all subjects completing gadolinium enhanced cMRI myocardial perfusion imaging, ¹³N-Ammonia PET perfusion imaging, ¹¹C-Acetate PET imaging and cMRI fibrosis imaging, the relationships between myocardial blood flow reserve, oxidative metabolism, and fibrosis will be evaluated using Spearman correlation. To account for potential confounders, multivariable linear regression models will be constructed with myocardial fibrosis or oxidative metabolism as the dependent variable, myocardial blood flow reserve as the primary independent variable with adjustments for age, gender, race/ethnicity, anti-hypertensive medications, systolic blood pressure, heart rate, body mass index, LVEF, LV end diastolic volume, LV mass, and study group. We will check model fit by residual plots. Prior to entry into regression models non-normally distributed variables will be appropriately transformed.

Statistical power for Aim 4: We present different margins of error for the Spearman correlation coefficient based upon different sample sizes and correlation coefficients in **Table 7**.

Based upon a sample size of 60 subjects, modest correlation coefficients of |0.40| to |0.50| would have 0.24 and 0.22 margins of error, respectively.

Sample Size	Correlation coefficient (absolute value)			
	0.2	0.3	0.4	0.5
40	0.32	0.31	0.30	0.28
50	0.28	0.28	0.26	0.24
60	0.26	0.25	0.24	0.22

4. Data Management

Patient clinical data is stored in Vanderbilt's electronic medical record. The hospital database is password protected and accessible only to the appropriate personnel. Research data will be labeled with a patient study code and stored in a separate research database. The code key connecting names to specific information will be available only to members of the research staff and will be kept in a separate, secure location.

The research data will be stored in a HIPPA-compliant manner in a REDCap database accessible to only the PI and key study personnel. Only those personnel that are directly involved in the study will have access to this database.

5. Safety Reporting

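### Replacing subjects with unreadable images restores the sample size but not the composition of the group, and the replacement rule discards the replaced subject and is not tied to gender

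*Combined protocol and SAP*

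**What the plan says.** Section 3, Analysis for aim 1, gives the missing-data rule: "Missing data will not be imputed as we will attempt to replace subjects with significant amounts of missing data due to uninterpretable images". The same sentence stands in Analysis for aim 2. Analysis for aim 3 takes it over by reference: "The analyses for aim 3 will be the same as for aim 2".

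The rule points back to details given earlier. The only such details are in Section 2.3, under 11C-Acetate PET. The trigger is "If the images are uninterpretable due to factors such as patient motion, attenuation artifacts, and/or inability to accurately gate images with ECG", and the consequence is "then the subject will be withdrawn from the study with attempts to replace the subject to maintain sample size". The cardiac MRI and 13N-Ammonia PET parts of Section 2.3, which supply the primary measures for Aims 1 and 3, contain no corresponding rule.

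The replacement text names neither study group nor gender. Section 2.2.1 says of the healthy group: "We will enroll volunteers matched on gender to the HFpEF group". The hypertensive group is likewise matched on gender. Gender is a covariate in the regression models, but the primary comparison is an unadjusted ANOVA or Kruskal-Wallis test.

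**The concern.** The plan gives replacement as its reason for not imputing. Replacement answers a different question. It returns the count to 20, but the substitute is by construction someone whose images could be read. If the subjects whose images fail differ in flow reserve, oxidative metabolism or T1 from those whose images succeed, the group mean stays biased at a full n of 20.

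Two features of the rule add to this:

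- **Whole-subject withdrawal.** A subject whose acetate images cannot be read is withdrawn from the study, not only from Aim 2. A readable flow reserve or T1 value in that subject would then be lost to Aims 1 and 3. Here the rule itself creates missing data.
- **No tie to gender.** If an HFpEF subject is replaced by one of the other gender after the controls are enrolled, the groups no longer match, and the primary test has no gender term.

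At stake is the HFpEF contrast in Aims 1 to 3. No count of replacements by group and no analysis that includes replaced subjects is planned, so the effect could not be judged afterwards.

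**Working it through.** **Inputs from the documents.** 20 subjects per group; one-way ANOVA at 0.05; SD of CFR 0.90; design difference (largest to smallest mean) 0.87 at 20 per group and 1.05 at 15 per group, each given as 80% power (Section 3, Statistical power for Aim 1, Table 4).

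**Assumptions, because the documents give no failure rate.** k = 2 or 4 of 20 HFpEF subjects are lost; losses occur in HFpEF only; the tendency to be lost correlates ρ = 0.3 to 0.5 with low CFR.

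**1. The plan's own figure.** The noncentrality is λ = n × Σ(mᵢ − m̄)²/SD². With the middle group at the midpoint, Σ(mᵢ − m̄)² = d²/2.

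- 15 per group, d = 1.05: λ = 15 × 1.05²/(2 × 0.90²) = 10.21. The F test has 79.4% power, against the stated 80%. The figure tied to loss of subjects is reproduced.
- 20 per group, d = 0.87: λ = 20 × 0.87²/(2 × 0.90²) = 9.34, power 76.4%. With the third group at an extreme it is 87.8%. The midpoint case is the baseline below.

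**2. What replacement does achieve.** If each group shrank without replacement, power for 0.87 would fall from 76.4% to 71.3% at 18 per group and 65.5% at 16 per group. Replacement prevents this loss.

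**3. What it does not achieve.** If the k subjects with the greatest tendency to fail are removed from 20, the mean of the rest is too high by ρ × SD × c, where c is the absolute sum of the k most extreme expected normal order statistics divided by (20 − k). This gives c = 0.182 for k = 2 and 0.333 for k = 4.

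| k | ρ | Bias in CFR units | Share of 0.87 |
|---|---|---|---|
| 2 | 0.3 | 0.3 × 0.90 × 0.182 = 0.049 | 6% |
| 2 | 0.5 | 0.5 × 0.90 × 0.182 = 0.082 | 9% |
| 4 | 0.3 | 0.3 × 0.90 × 0.333 = 0.090 | 10% |
| 4 | 0.5 | 0.5 × 0.90 × 0.333 = 0.150 | 17% |
| any | 0 | 0 | 0% |

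Substitutes pass the same filter. With a failure fraction q = k/20, their expected shift is ρ × SD × φ(z)/(1 − q), where z is the normal quantile at q:

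- q = 0.10: φ(z)/(1 − q) = 0.195, shift 0.053 to 0.088.
- q = 0.20: φ(z)/(1 − q) = 0.350, shift 0.094 to 0.157.

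These are close to the table, so filling the cells leaves the bias about where it was.

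**4. Effect on power at a full 20 per group.** The HFpEF mean is moved up by the shift in step 3 and the other two means are held. Power falls from 76.4% to 71–67% at q = 0.10 and to 66–59% at q = 0.20.

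**5. Gender.** Each opposite-gender replacement moves a group of 20 by 1/20 = 5 percentage points. If replacement ignored gender and half of the candidates were women (assumed), a single replacement would change the mix with probability 50%.

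**The case against.** The strongest reply is that the eligibility criteria already make this an imageable population. Claustrophobia, inability to lie flat, contraindication to regadenoson and inability to complete imaging over two consecutive days are all exclusions. Table 2 excludes significant arrhythmia in HFpEF and caps weight at 350 lbs. The analyzing investigator is blinded to group. The bias shown is also below one standard error of a group mean (0.90/√20 = 0.20), and under the assumed direction it runs toward no difference.

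Much of this stands, and it rules out several stronger readings:

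- **A reader might infer that unreadable scans cluster in the sickest HFpEF subjects.** The documents do not say so. HFpEF subjects must be symptomatic, and they are not subject to the obesity criterion applied to controls, so the idea is plausible. It remains an assumption.
- **A reader might infer that scans not done are a large uncovered category.** The exclusions remove most of the obvious causes. Some failures remain, and they have no rule.
- **A reader might infer that the plan has no missing-data handling at all.** Aim 4 states a completers set ("For all subjects completing gadolinium enhanced cMRI myocardial perfusion imaging"), and the power text allows a 25% loss, though for precision only.
- **A reader might infer that the gender match is generally unprotected.** Twenty per group implies replacement within group, and the matching rule also governs a replacement control. What remains exposed is a late HFpEF replacement, in the unadjusted test only, since the regressions include gender.

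The reply does not rescue the stated reasoning. Eligibility criteria and blinded reading reduce the number of failures; they do not make the failures unrelated to outcome. A shift smaller than a standard error is still systematic and is not reduced by adding filtered subjects.

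**Conclusion.** The point holds in a limited form. Replacement is a sound way to protect precision, but it is not a reason to leave missing values unexamined. Whole-subject withdrawal after an unreadable acetate scan also discards measures that may be usable for the other aims.

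The size is modest and conditional: 0.05 to 0.15 CFR units under the stated assumptions, and none if readability is unrelated to flow reserve. Only CFR was worked through; for K_mono and T1 the reasoning is the same but no figure is claimed. The gender effect is 5 percentage points per opposite-gender replacement and arises only when an HFpEF subject is replaced after controls have been enrolled. A change is worth making because it costs little and without it the effect could not be seen.

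**What to change.** Amend the 11C-Acetate PET part of Section 2.3 and the missing-data sentence in Analysis for aim 1 and Analysis for aim 2 (Aim 3 follows by reference) to state that:

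1. A subject who lacks a primary measure because a scan was unreadable, stopped or not done may be replaced by a subject of the same group and gender.
2. The replaced subject is not withdrawn for this reason, and every measure observed in that subject enters the analysis for its aim. The data-removal rule in Section 5 still applies to subjects who choose to withdraw.
3. The primary analysis uses observed values.
4. One simple sensitivity analysis includes the replaced subjects. For Aim 1 it could use the other modality's flow reserve where available. The relation between the MRI perfusion reserve index (MPRI) and CFR is itself a secondary hypothesis, so it should be shown in the data before it is relied on.
5. Replacements are reported by group and reason.

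Step 2 recovers values that the present rule throws away. It does not recover a measure whose own scan failed; step 4 addresses that. An imputation model with many predictors is not needed and would be fragile at 20 per group.

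The cost is a change of wording and one extra analysis on data already collected. Same-gender substitutes may take slightly longer to find, and the number analysed may differ between measures.
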